- 2) Major concomitant medical illness including planned antibiotic treatment for greater than 3 days or NPO status;
- 3) Infants who are being placed for adoption;
- 4) Infants in significant pain requiring narcotic medication for comfort (for example those with a fracture);
- 5) Infants whose maternal UDS at the time of delivery is positive for any other drug of abuse beside opiates;
- 6) Mother with hearing or language impairment.

Comparison Group:

Inclusion Criteria:

- 1) Baby is diagnosed with neonatal abstinence syndrome;
- 2) Newborns \geq 37 0/7 weeks gestation;
- 3) Newborns transferred to JHACH within 72 hours from birth;
- 4) Newborns \geq 2.5 kg weight at birth;
- 5) Informed parental consent.

Exclusion Criteria:

- 1) Infant not requiring pharmacologic treatment for NAS;
- 2) Major congenital anomalies;
- 3) Major concomitant medical illness including planned antibiotic treatment for greater than 3 days or NPO status;
- 4) Infants who are being placed for adoption;
- 5) Infants in significant pain requiring narcotic medication for comfort (for example those with a fracture);
- 6) Mother with hearing or language impairment;
- 7) Infants known upon admission who will be placed into state custody or sheltered.

Principal Investigator: [name], MPH

Application Number: IRB00107690

Study Procedures

- a. **Study design, including the sequence and timing of study procedures** (distinguish research procedures from those that are part of routine care).

General Design Issues:

The proposed demonstration project is a non-randomized, un-blinded feasibility study. A prospective cohort study design will be implemented.

Eligibility and Enrollment Process:

a) **Methadone Treatment Group:** Mothers who meet the criteria for enrollment in the demonstration project will be identified by the Operation PAR personnel during the last month of pregnancy. Such individuals will be approached by PAR personnel to determine their willingness to learn more about the methadone study. If they are interested, their contact information will be given to a study team member at Kids Home Care. The Kids Home Care study team member will contact the mother via telephone to discuss the study and may provide mother with a copy of the informed consent in order to give the mother ample time prior to delivery to ask questions of the study team.

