^e After initiation of methadone treatment and prior to discharge during the weaning phase of narcotic treatment

^f Home visit or phone interview

Principal Investigator: [name], MPH

Application Number: IRB00107690

Comparison Group:

Study Intervention	Enrollment	While inpatient	6 – 8 weeks of age
Informed Consent	X		
The Postpartum Bonding Questionnaire (PBQ)		X ^a	X ^b
Edinburgh Postnatal Depression Scale (EPDS)		X ^a	X ^b

^a After initiation of standard of care narcotics for treatment of NAS and prior to discharge during the weaning phase of narcotic treatment

^b Administered either through a home visit by Kids Home Care or via a phone interview conducted by a study team member

Routine (usual) care for infants born to mothers with a history of opiate use: All infants have routine scoring with the modified Finnegan scoring tool approximately every 3 to 4 hours per standard of care for signs of NAS. Infants will be managed with comfort, non-pharmacological measures. Initiation of medical treatment will take place when 2 consecutive Finnegan scores are > 8. Escalation of treatment and weaning will follow set protocols. Vital signs, blood pressures and cardiorespiratory monitoring follow the NICU standard of practice. Outpatient neurodevelopmental follow-up is offered at 1 and 2 years of age.

Comparison Group:

The comparison group of mother/baby dyads will receive standard of care treatment. The study interventions in this group are limited to the bonding and depression assessments. All other data required for analysis of the study aims can be abstracted from the baby's medical record as it is part of standard clinical care.

Methadone Treatment group:

A. Infant participants will receive the following services not part of the standard of care at JHACH:

- a) Initiation of the commercially available methadone treatment instead of morphine as pharmacologic treatment (see methadone treatment below);
- b) Maternal education on recognizing signs and symptoms of withdrawal as well as understanding and performing adequate Finnegan scoring. Specifically, mothers will be taught how to demonstrate tone and tremors on Physical exam.
- c) Provision of close psychological and emotional support to mothers

Principal Investigator: [name], MPH

Application Number: IRB00107690

- d) Facilitation of prolonged maternal physical presence at her infant's bedside

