- a. **Primary outcome variable:** Length of Stay (LOS)

- b. **Additional outcomes of interest to be examined:**

- 1) Maternal bonding measured by the Postpartum Bonding Questionnaire (PBQ);
- 2) Depressive symptomatology measured by Edinburgh Postnatal Depression Scale (EPDS);
- 3) Hospital readmission within 30 days;
- 4) Weight gain of greater than 15% above Birth Weight at 30 days of age;
- 5) Age appropriate development as screened by the Ages and Stages questionnaires.

- c. **Statistical plan including sample size justification and interim data analysis:**

Demographic and clinical characteristics of participants will be summarized using means with standard deviations (SD) or median with interquartile ranges for continuous variables and counts and percentages for categorical variables. The primary outcome, length of stay, will be summarized using mean (SD) or median and interquartile range and will be compared to the comparison group using the t-test or Wilcoxon rank sum test as appropriate. For the secondary outcomes, the scores on the postpartum bonding questionnaire or the Edinburgh Postnatal Depression Scale will be summarized using means (SD) and compared to other patients in the comparison group using independent two-sample t-test. The proportion of participants that are readmitted within 30 days or with a weight gain of greater than 15% above birth weight will be compared to the comparison group using a Chi-squared or Fishers exact test as appropriate. Among the methadone cohort, we will calculate percentage of infants with age appropriate development at 4, 8 and 12 months. We anticipate that 25 mother-child dyads in each group will be available for the study. We expect that the mean LOS in the comparison group will be around 25 days (based on historical data). This sample size will allow us to estimate differences in LOS of >4 days with sufficient power (80%) at an alpha of 0.05, assuming a standard deviation of 5 days for both groups.

Early stopping rules:

Infant: requiring therapy with a second drug

Parents: desire to remove the infant from the study at any time or when infant is transferred to another hospital.

7. Risks

- a. **Medical risks, listing all procedures, their major and minor risks and expected frequency:**

Principal Investigator: [name], MPH

Application Number: IRB00107690

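### The non-randomised primary comparison of length of stay is unadjusted, so any difference in initial infant severity between the two differently selected groups passes straight into the estimate

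*Combined protocol and SAP*

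**What the plan says.** Under General Design Issues: "The proposed demonstration project is a non-randomized, un-blinded feasibility study". Section 6.c names LOS as the primary outcome and says that it "will be compared to the comparison group using the t-test or Wilcoxon rank sum test as appropriate". Baseline characteristics are to be summarised, but no analysis uses them.

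The sample size statement in 6.c reads "This sample size will allow us to estimate differences in LOS of >4 days". Its stated basis is 25 dyads per group, an SD of 5 days in each, 80% power and a 0.05 significance level.

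On the data available, section 4 sets the same minimum gestational age (37 weeks) and birth weight (2.5 kg) in both groups, so both variables are known for every infant. The paragraph on routine care says "All infants have routine scoring with the modified Finnegan scoring tool approximately every 3 to 4 hours". Drug treatment starts after two consecutive scores above 8, both in routine care and in the Demonstration Study Methadone Protocol. Comparison-group data other than the maternal questionnaires come from the medical record.

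On selection, only the methadone group requires maternal care at Operation PAR, judged compliance, a stable maternal dose, prescreening by the project team, and a delivery drug screen negative for drugs of abuse other than opiates.

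**The concern.** With no randomisation, nothing in the design makes the groups alike in severity when treatment starts. The methadone group's maternal criteria could plausibly shift infant severity, although the documents do not say in which direction or by how much.

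Severity is also a plausible predictor of LOS on the protocol's own terms. The 24-hour Finnegan average decides weaning, holding and escalation, and discharge on methadone depends on the dose reached and on a history of weaning. The shared treatment trigger sets a floor on severity at the start of treatment, not a ceiling.

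At stake is the meaning of the primary result. A t-test or rank sum test cannot separate a methadone effect from a difference in how ill the infants were. In an unblinded study, covariates chosen after the data are seen would not be a convincing repair.

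**Working it through.** **Inputs from section 6.c.** n = 25 per group, SD = 5 days, difference = 4 days, alpha = 0.05. Sidedness is not stated; two-sided is assumed because it reproduces the stated 80% (one-sided would give 88%).

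**Step 1: the plan's own figure.**
- Sample size: 2 × (1.96 + 0.84)² × 5² / 4² = 24.5, so 25 per group.
- Standard error of the difference: 5 × √(2/25) = 1.414 days. Noncentrality: 4 / 1.414 = 2.83.
- Power: 80.7% by the normal approximation and 79.1% by the noncentral t with 48 df. A simulation of the rank sum test on normal data gives about 76.5%.

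The statement reproduces for the t-test. It contains no arithmetic error.

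**Step 2: bias of the unadjusted difference.** Let R² be the share of within-group LOS variance explained by initial severity, and d the systematic difference in severity between groups in SD units. Neither is in the documents; both are assumed.

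Bias = √R² × d × 5 days. The error rate is the chance that the two-sided t-test rejects when the true effect is zero, with noncentrality bias / 1.414.

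| R² | d | Bias (days) | Two-sided error |
|---|---|---|---|
| 0.1 | 0.3 | 0.47 | 6.2% |
| 0.1 | 0.5 | 0.79 | 8.5% |
| 0.2 | 0.5 | 1.12 | 12.1% |
| 0.3 | 0.5 | 1.37 | 15.8% |
| 0.3 | 0.8 | 2.19 | 33.0% |

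For example, √0.2 × 0.5 × 5 = 1.12 days, and 1.12 / 1.414 = 0.79. Against the 4-day difference in the sample size statement, 1.12 days is 28% and 2.19 days is 55%.

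**Step 3: what adjustment does to precision.** The ratio of adjusted to unadjusted variance is (1 − R²) / (1 − Rg²), where Rg² is the share of group membership that the covariates explain. Write rho = √R², again assumed.

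- Three covariates (45 residual df) with chance imbalance only, by simulation with 20,000 runs: power for 4 days is about 80% at rho 0.3 and 86–87% at rho 0.5, against 79% unadjusted. Below rho of about 0.25 the adjusted test is no better.
- Covariates explaining 20% of group membership: at rho 0.3 the ratio is 0.91 / 0.80 = 1.14 and power is about 74%. At rho 0.4 it is 0.84 / 0.80 = 1.05 and power is about 77%. Both are below the unadjusted test.

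**Step 4: is power the problem?** The Abstract hypothesises a fall from 25 to under 15 days. For 10 days the noncentrality is 10 / 1.414 = 7.07, and unadjusted power exceeds 99.9%.

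**The case against.** The strongest reply is that this is a feasibility study of 50 infants, not meant as a well-controlled study for the FDA (section 5.b), and that simple tests suit that size. Four specific points follow.

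- **Precision.** A reader might infer that the unadjusted test necessarily wastes power. The documents do not support that: they give no correlation between any baseline variable and LOS. Step 3 shows that adjustment can also widen the interval, and step 4 that power is ample for the hypothesised effect. This objection stands, and the case for adjusting rests on bias.
- **Prognostic value.** No passage links pre-treatment scores to LOS. The weaning rules use scores taken on treatment, gestational age and birth weight are truncated by eligibility, and the shared trigger narrows the spread of severity. This is fair and is why R² is shown as a range. It makes the bias uncertain, not absent.
- **Availability.** A reader might assume a full 24 hours of scores before any opioid for every infant. An infant who soon reaches two scores above 8 may have only two or three, and infants may arrive up to 72 hours after birth. The documents do not say whether earlier scores reach the chart or whether an opioid can start before transfer. This stands, and it governs how the covariate must be defined.
- **Residual confounding.** Three infant variables do not address PAR care and compliance, maternal dose stability, child-protection status or other drug exposure. Methadone infants may also go home while still on drug, which shortens LOS whatever their severity. This stands too. It limits the claim that an adjusted result can make, but does not justify leaving measured severity out.

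**Conclusion.** The gap is real and should be closed. The primary LOS comparison is non-randomised and unadjusted, although infant severity data are collected routinely in both groups. Under the assumed values in step 2, the bias runs from about 0.5 to 2.2 days and the two-sided error from about 6% to 33%. These figures illustrate size and do not predict it, since neither R² nor d is in the documents. The bias could favour either group. At a true 10-day fall, a bias of this order would change the size of the estimate more than its sign; near the 4-day difference used for the sample size, it could change the conclusion.

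Three stronger readings are not supported. The sample size is not miscalculated. A loss of precision from the simple test is not established. Adjustment for infant severity would not make the groups comparable on maternal selection.

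**What to change.** In section 6.c, make the main LOS analysis a linear model for LOS in days, with robust or bootstrap standard errors and these terms: group, pre-treatment Finnegan score, gestational age and birth weight. Define the score so that every treated infant has it: for example the mean of the two consecutive scores that triggered treatment, or of all available scores before the first opioid dose. Choose one definition now, and say how an infant who received an opioid before transfer would be handled.

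Report the adjusted difference with its 95% CI as the main estimate, and keep the t-test or rank sum test as the unadjusted supporting result. State that a gain in precision is possible but not assured, and that confounding by the maternal criteria in section 4 remains. Keep the covariate list short, because there are only 50 infants.

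The cost is a few sentences in 6.c, abstraction of early scores from the chart, three degrees of freedom, and possibly a wider interval if the covariates differ between groups.

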This demonstration project has the potential to improve short and long term outcome of infants suffering from NAS while decreasing the cost of their care. It aims at doing so by 1) reaching out to qualifying mothers prior to delivery; 2) empowering those mothers during their infant hospital stay by further educating them on NAS and means of comforting and easing their infant's withdrawal symptoms; 3) discharging infants home while still on narcotic treatment under very close medical supervision until complete weaning is achieved; 4) ensuring a safe home environment and healthy maternal involvement throughout withdrawal and for a year after cessation of medical treatment.

Principal Investigator: [name], MPH

Application Number: IRB00107690

2. Objectives

Primary Objective: Compare the LOS of NICU infants with NAS treated with methadone with historical data and a comparison group of NICU NAS infants treated with a different narcotic agent.

Secondary Objectives:

- 1) Compare maternal bonding between methadone treated infants and those treated with a different narcotic,
- 2) Assess if methadone treatment leads to decreased maternal depressive symptomatology as compared to treatment with other narcotics;
- 3) Study whether methadone treatments leads to safer transition to home with no readmissions to the hospital within 30 days for NAS-related reasons;
- 4) Compare proportions of children who gain weight (greater than 15% above birth weight) at 30 days of age between methadone treated and non-treated infants;
- 5) Compare the incidence of providing breast milk (> 50% of nutritional needs) at 30 days of age between methadone treated and non-treated infants;
- 6) Assess the age appropriate infant development at 4, 8 and 12 months of age among the methadone treatment group;
- 7) Determine the response percentage of mothers who are screened as eligible by PAR officials and who agree to participate in the demonstration project;
- 8) Assess the drop out percentage of mothers who agree to participate but do not follow through with home discharge for continued care;
- 9) Quantitate the proportion of mothers who feel comfortable with home care of their infant at discharge;
- 10) Monitor the readiness of mothers to assess infant on 3 to 4 hours intervals while at home;
- 11) Determine the compliance rate with the Johns Hopkins All Children's Hospital (JHACH) pediatrician visits.

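### Testing 30-day weight only as a yes/no at 15% above birth weight, with about 25 infants per group, gives up power that the same two weights could provide

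*Combined protocol and SAP*

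**What the plan says.** Section 2 (Objectives), secondary objective 4, sets the comparison: "Compare proportions of children who gain weight (greater than 15% above birth weight) at 30 days of age". Section 6.b lists the outcome in the same binary form: "Weight gain of greater than 15% above Birth Weight at 30 days of age". Section 6.c states the test, for the share of infants "with a weight gain of greater than 15% above birth weight will be compared to the comparison group using a Chi-squared" test, and names Fisher's exact test as the alternative.

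On size, section 6.c says "We anticipate that 25 mother-child dyads in each group will be available for the study". The only power statement concerns length of stay (LOS): "This sample size will allow us to estimate differences in LOS of >4 days with sufficient power (80%) at an alpha of 0.05". It takes the SD of LOS as 5 days in each group.

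The documents give no analysis of weight or percent gain as a quantity, no adjustment for birth weight, no reason for the 15% cut, no expected proportion and no power for this outcome. In the same paragraph LOS and the bonding and depression scores are analysed as quantities, although the bonding and depression scales have action thresholds elsewhere in the protocol.

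Neither schedule of events lists a weight at 30 days. Apart from the two maternal questionnaires, comparison-group data come from the infant's chart: "All other data required for analysis of the study aims can be abstracted".

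**The concern.** Birth weight and 30-day weight are continuous, and both are needed before an infant can be classified. The planned test then treats gains of 14% and 16% as opposites, and gains of 16% and 40% as the same. With about 25 per group there is little information to spare.

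Methadone infants go home while still being weaned, and section 7 notes that feeding problems are common during withdrawal. Adverse events are collected only in infants who receive study drug. Thirty-day weight is therefore one of the few infant outcomes compared between the groups. A non-significant chi-squared or Fisher result could be taken as reassurance about growth, whereas a mean difference with a confidence interval would show what had and had not been ruled out.

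**Working it through.** **The plan's own figure.** Inputs from section 6.c: difference 4 days, SD 5, alpha 0.05 (two-sided assumed, as sidedness is not stated), power 80%.

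- n per group = 2 × (1.960 + 0.842)² × (5/4)² = 24.5, rounded up to 25.
- Power at 25 per group = Φ(0.8 × √(25/2) − 1.960) = Φ(0.868) = 80.7%. With the noncentral t it is 79.1%.

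The LOS statement reproduces.

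**Assumptions for weight.** The documents supply none. I take percent gain as normal with SD 8 points in both groups, and vary the control mean m over 12-25%. The true shift d is 0.8 SD (the plan's LOS ratio 4/5, or 6.4 points here) or 0.5 SD (4 points). There are 25 infants per group and the test is two-sided at 0.05.

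**Continuous analysis.** A t-test on percent gain has 79% power at d = 0.8 and 41% at d = 0.5.

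**Binary analysis, methadone infants gaining less.** The proportion above 15% is Φ((m − 15)/8) in controls and Φ((m − 15)/8 − d) in the methadone group. Power is the sum of the two binomial probabilities over every 2×2 table that the test rejects (chi-squared without continuity correction).

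| Control mean gain | Control above 15% | Methadone above 15%, d = 0.8 | Chi-squared / Fisher | Methadone above 15%, d = 0.5 | Chi-squared / Fisher |
|---|---|---|---|---|---|
| 12% | 35% | 12% | 52% / 37% | 19% | 26% / 16% |
| 15% | 50% | 21% | 60% / 47% | 31% | 31% / 21% |
| 20% | 73% | 43% | 63% / 52% | 55% | 29% / 20% |
| 25% | 89% | 67% | 50% / 35% | 77% | 22% / 12% |

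**Methadone infants gaining more, d = 0.8.** Same formula with +d:

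- m = 12%: 65% / 54%
- m = 15%: 60% / 47%
- m = 20%: 45% / 30%
- m = 25%: about 17.5% / 3%, where 89% of controls already pass against 98% of methadone infants.

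**Best case for the cut.** If 15% fell midway between the group means (34% against 66% above it), power would be 65% / 54% at d = 0.8 and 33% / 23% at d = 0.5. At d = 0.8, 80% power at that cut needs 40 per group, against 25 for the continuous analysis. In large samples a cut keeps φ(c)²/[q(1 − q)] of the information, where q is the proportion on one side of the cut c. That is 64% at a 50/50 split, 58% at 30/70, 49% at 20/80 and 34% at 10/90.

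**The case against.** Several points on the other side stand.

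- **Size is assumed.** The documents give no mean, SD or expected proportion for weight gain. Only the direction of the loss is secure, and only for a roughly normal shift.
- **Importance is limited.** Weight is the fourth of eleven secondary objectives in a non-randomised feasibility study. Safety is handled through adverse events, an independent monitor and stopping rules. Nowhere does the plan say that a non-significant weight test will be read as equivalence. A reader might infer that weight is a principal check against harm, but the documents do not give it that role.
- **The cut may be clinically useful.** If so, it can still be reported.
- **The weights are required, not already in hand.** Paediatrician visits appear only in the methadone schedule. Comparison infants are expected to stay about 25 days, so day 30 may fall after discharge. For infants taken off treatment, data are assured only to final hospital discharge. This gap affects the binary outcome equally.

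A reader might also infer that the test could hardly detect poorer growth, or has almost no power once most infants pass 15%. The documents do not support that. The lowest figures above, about 17.5% and 3%, belong to a methadone group that gains more, near a ceiling. When methadone infants gain less and most controls pass, the shift moves infants back towards the cut: at a control mean of 25%, power is 50% / 35%. Harm-direction power would fall to very low values only with control means beyond the range used here, and nothing in the documents places the mean there.

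**Conclusion.** The point holds as a modest, avoidable loss of precision on a secondary outcome. If methadone infants gain 0.8 SD less, power falls from 79% to 50-63% (chi-squared) or 35-52% (Fisher) over control means of 12-25%. If they gain 0.5 SD less, it falls from 41% to 22-31% or 12-21%. The loss is larger if they gain more and most controls already pass the cut.

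These figures assume normal percent gain, SD 8 points, equal spread and 25 weighed infants per group. At a 0.8 SD shift, no position of the cut gets above 65% or 54%. Even the continuous analysis is weak for a 0.5 SD difference, which is a further reason to report an interval rather than rely on a test. The primary LOS comparison and its power statement are not affected.

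**What to change.** In section 6.c, make the test for objective 4 a linear regression of 30-day weight on group, with birth weight and exact age at weighing as covariates. Report the adjusted mean difference with its 95% confidence interval, and keep the proportion above 15% in each group as a descriptive figure. Align secondary objective 4 and section 6.b with this.

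State one weighing window around day 30 and one data source for both groups, and record age at weighing. Report how many infants in each group have a weight in the window, because missing weights affect either analysis.

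The cost is revised wording, slightly more analysis work and one extra recorded item (age at weighing). The model uses the two weights that the present endpoint already requires. It adjusts for birth weight and age at weighing only and does not remove other differences between non-randomised groups.
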